**Developing a Tool to Support Shared Decision-Making Post-Concussion  
Between Adolescents, Parents and Clinicians**

**NCT Number:** NCT04777864

**Document Date:** 03/17/2022

*Due to the smaller sample recruited we simplified our analytic plan to focus on between-condition comparisons for the primary decision-related outcomes and no subgroup comparisons.*

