**Aim 3 (continued):** Second, this aim will conduct usability testing with clinicians (including pediatricians and family medicine providers) for a clinician-specific decision aid. The findings from Aim 1 and Aim 2 will help inform the creation of a clinician-specific decision aid. Findings from this aim will be used directly in Aim 4.

**Aim 4:** This aim has two cohorts:

Aim 4a: Cohort 1 will evaluate how shared decision making currently occurs in a clinical appointment. This data will then be used to compare need and impact of the intervention group in Aim 4b.

Aim 4b: Cohort 2 includes a pilot random control trial (RCT) of all three decision aids (i.e., parent, adolescent, clinician) to assess intervention efficacy of all decision aids in aiding family shared decision making in returning to sport post-sport related concussion.

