**Aim 3:** This aim involves semi-structured interviews, and usability testing with clinicians as described below. Usability testing will be informed by the interviews and will be submitted for IRB review after the interviews are complete. Participants (i.e., clinicians) will participate in a 60-minute interview, either in person or online. Prior to the start of the interview, participants will review an information sheet about the study that will either be emailed to them (if session is conducted online) or printed and handed in person (if session is conducted in person). Then, they will be interviewed (inclusive of cognitive interviewing, qualitative interviewing,) about specific clinician feedback on how to create a decision aid effectively for their use. All interview data will be audio recorded. All documents used in this aim can be found in the attachment section of Click. All interviews conducted online will be done so through an online platform (i.e., Zoom) and their online session will be recorded.

**Aim 4a and b:** In the first data collection cohort (Aim 4a), there will be no change to the nature of provider communication with families seeking care for their child's concussion. In the second cohort (Aim 4b), the study team will share the respective decision aids with the family and let them know to complete them before their appointment. After both the parent and adolescent complete their respective decision aids, a member of the study team will insert the clinician tool link in the patient's chart and/or send a message with the link for the clinician to review, prior to the appointment.

Data will be collected about the experience that families have discussing the decision of what sports and activities they participate in after they recover from their injury and using their respective decision aids (intervention only). Survey data will be collected from parents and adolescents at several time points (baseline, post-visit(s) up to and including their final visit, 3-months after initial visit). Survey data will also be collected from healthcare providers about their experiences sharing information with families and using the tool (intervention only) over this time period. Data will be collected at one time point (after a patient of the healthcare provider has completed the tool).

**5.3.** Data sources that will be used to collect data about subjects:

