### 10.4. Power analysis:

**Aim 1:** This data is primarily being assessed for qualitative responses; therefore, no power analyses are being assessed.

**Aims 2 & 3:** This data is primarily qualitative, and thus a power calculation is not appropriate.

**Aim 4a and b:** We anticipate enrolling 20 families per study phase; allowing for 15% attrition an estimated 17 per phase would complete the study. Conservatively estimating 15 families per phase, we will have  $\geq 80\%$  power to detect a difference in decisional regret (range: 0 to 100 points) as small as 7.1, 3.0 and 1.2 points, for SD = 12, 5, and 2, respectively. These estimates assume an alpha of 0.05 and SD ranging from 1-12. The data from the healthcare provider survey is primarily qualitative, and thus a power calculation is not appropriate.

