#### 14. Data Analysis/Management

##### 14.1. Data analysis plan, including statistical procedures:

**Aim 1:** Survey responses will be reviewed with a focus on the psychometric properties of items and scales (e.g., how are items distributed), as well as evaluate what answers are correlated. We will compare responses across key characteristics (e.g., clinician characteristics, beliefs) to determine what key beliefs and feedback are across all clinicians, parents, and adolescents.

**Aim 2 & 3:** Thematic analysis will be used to systematically code transcripts and identify emergent themes. Qualitative data will be digitally recorded and transcribed verbatim and coded for relevant themes using a thematic analysis approach. Coded segments may be entered into a qualitative coding software (e.g., Dedoose) to facilitate analysis or will be analyzed by quantified elements. Data will continue to be conducted until emergent results iteratively inform and clarify the final version of the decision aids.

**Aim 4a and b:** We will compare socio-demographic (e.g. age, sex, health literacy) and clinical characteristics (e.g. concussion history and severity at baseline) between the control and intervention groups. Differences in primary decision process and quality outcomes will be compared between treatment and control conditions using Structural Equation Modeling, where parent and child measures will be examined in parallel. Family level non-independence will be modeled by residual covariances between parent(s) and child measures. Outcomes will be pooled across the retirement recommended and equipoise conditions as decision process and quality measures are equally relevant in both conditions. Secondary analyses related to health behaviors (contact sport participation and physical activity) and health status outcomes at Time 3 will be compared between treatment and control conditions using logistic regression.

**Dyadic and triadic analyses.** Dyadic/triadic concordance will first be described using contingency tables. Next, actor-partner interdependence models will be used to assess the effects of each family member's decision process measures on their own decision quality measures and the rest of the family's decision quality measures ("partner" effects). Healthcare provider survey responses will be reviewed and compared to determine key beliefs and feedback across all healthcare providers.

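### Aim 4 names no deciding primary outcome, reporter or time point and no multiplicity rule, so a claim resting on any significant primary contrast would have an error rate above the 0.05 used in 10.4

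*Combined protocol and SAP*

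**What the plan says.** For Aim 4, section 14.1 states: "Differences in primary decision process and quality outcomes will be compared between treatment and control conditions using Structural Equation Modeling". Both reporters enter this comparison, which the plan describes as one "where parent and child measures will be examined in parallel". On the dependence within a family it adds: "Family level non-independence will be modeled by residual covariances between parent(s) and child measures". It lists no measures and sets no significance level or success rule. It ties the secondary outcomes to Time 3 but gives the primary comparison no time point.

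Section 5.2 collects parent and adolescent surveys "at several time points (baseline, post-visit(s) up to and including their final visit, 3-months after initial visit". Section 3.1, headed as the endpoints section, gives only recruitment targets and the end of participation for Aim 4.

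Section 10.4 claims at least 80% "power to detect a difference in decisional regret (range: 0 to 100 points", and says: "These estimates assume an alpha of 0.05". It does not call regret the primary outcome, and it names neither reporter nor time point. Section 14.1 does not mention regret.

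Section 1.1 describes Aim 4b as a pilot "to assess intervention efficacy of all decision aids in aiding family shared decision making". Section 1.2 says that the research is qualitative and has no hypotheses to test. The cover note, written after a smaller sample had been recruited, says that the team "simplified our analytic plan to focus on between-condition comparisons for the primary decision-related outcomes and no subgroup comparisons". The primary outcomes are still plural and unnamed there.

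**The concern.** The wording implies at least one process measure and one quality measure, each for two reporters, and possibly at more than one time. These contrasts can disagree: the parent result may differ from the adolescent result, a process measure from regret, the final visit from 3 months. The plan has no rule for which of them answers Aim 4b.

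Two things follow. A reader cannot tell from the plan which result the efficacy statement rests on. And if any significant primary contrast is accepted as support, the 0.05 in 10.4 is not the error rate of the conclusion. The cover note sharpens this, because the analysis was revised after recruitment and the deciding contrast was still left open.

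**Working it through.** **1. The plan's own figures.** The documents state no family-wise error rate. The only related figures are the detectable differences in 10.4: 7.1, 3.0 and 1.2 points for SD 12, 5 and 2, at 15 families per phase, alpha 0.05 and at least 80% power. For a two-sided comparison of two means,

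detectable difference = (1.960 + 0.842) × SD × √(2/15) = 1.023 × SD,

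which gives 12.3, 5.1 and 2.0 (normal approximation), or 12.7, 5.3 and 2.1 with the t distribution. The stated values do not reproduce. Power for the stated differences at 15 per phase is about 35% (t distribution). This is a separate matter from multiplicity, but it limits what the fix can reuse.

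**2. How many tests?** The count is not in the documents, so these are assumptions:

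- 2 tests: regret alone, parent and adolescent.
- 4 tests: one process and one quality measure × two reporters, at one time point. This is the smallest set that fits the wording of 14.1 with both classes present.
- 8 tests: the same four at two time points. Section 5.2 shows surveys at several times, but the documents do not say that each primary measure is analysed at each of them.

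**3. Independent tests.** The chance of at least one significant difference under no effect is 1 − 0.95^k, and for differences in one given direction 1 − 0.975^k:

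- k = 2: 9.8% and 4.9%
- k = 4: 18.5% and 9.6%
- k = 8: 33.7% and 18.3%

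**4. Correlated tests.** Simulation under no effect: 15 v 15 families, equicorrelated normal outcomes, two-sample t-tests at two-sided 0.05.

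| Tests | Correlation | Either direction | Favouring the aids |
|---|---|---|---|
| 2 | 0.5 | 9% | 4.5% |
| 4 | 0.5 | 16% | 8% |
| 8 | 0.5 | 26% | 13% |
| 2 | 0.9 | 7% | 3.5% |
| 4 | 0.9 | 9.5% | 4.7% |
| 8 | 0.9 | 12% | 6% |

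A single two-sided test has 5% and 2.5% in these columns. Every row exceeds them.

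**5. Does the planned model deal with this?** Residual covariances describe how parent and adolescent scores move together. They do not limit the number of condition effects that may be read as the answer, so they do not control the error rate across those effects.

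**6. Would a joint parent-adolescent test hold 5% at this size?** For a test of two condition effects with 15 per phase (N = 30, 28 within-group degrees of freedom), the Hotelling statistic T² satisfies (27/56) × T² ~ F(2, 27), which is exact under normality. The usual large-sample versions compare with the chi-square(2) 5% point, 5.99:

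- Likelihood ratio: 30 × ln(1 + T²/28) > 5.99 rejects in 6.7% of null trials.
- Wald with the maximum-likelihood covariance: (30/28) × T² > 5.99 rejects in 8.6%.

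So the F reference has to be specified.

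**The case against.** The strongest defence is that this is a pilot of 20 families per phase. Section 1.2 disclaims hypotheses, 14.1 sets no significance threshold, and nothing says that one significant result suffices. Strict family-wise control is less clearly required here than in a confirmatory trial. That stands as a limit on how serious the point is. It does not remove it: the same document sets an alpha and a power target, labels outcomes primary, specifies a comparison of conditions and states an efficacy aim. Either one contrast carries that aim, or the aim should not be worded as efficacy.

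A reader might infer that the plan's chance of a false efficacy finding is 15 to 26%. The documents do not support that. It needs 4 to 8 tests at correlation 0.5, and neither figure is given. It also counts differences that favour the control cohort, which are not false efficacy findings. It further takes 0.05 from the power paragraph as the level of each test, and uses separate t-tests in place of the planned structural equation model.

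A reader might also take the cover note to remove only subgroup comparisons. Its focus on between-condition comparisons may equally drop the actor-partner and concordance analyses. It does not say whether the structural equation model is kept. It does not name a primary outcome on either reading.

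**Conclusion.** The point holds in a conditional form. The defect that rests on the text alone is that Aim 4 has no deciding outcome, reporter or time point and no multiplicity rule, while 10.4 considers one outcome at alpha 0.05. The size depends on assumptions: if any significant primary contrast at 0.05 is taken as support, the illustrative rates at correlation 0.5 are about 9%, 16% and 26% for 2, 4 and 8 tests in either direction, roughly half that for results favouring the aids. Stronger correlation lowers the rates, and more measures or time points raise them. The direction of the problem does not depend on these choices, but no single percentage can be called the plan's error rate. For a pilot this should be corrected, and wording is enough to correct it.

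**What to change.** In 14.1 and the cover note:

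- Name decisional regret, the only outcome sized in 10.4, as the single primary outcome at one stated time point. The documents fix no time for it, so this is the sponsor's choice. The 3-month survey is one example.
- Test the 4b v 4a difference once, for parent and adolescent jointly, with a small-sample F (Hotelling) reference at 0.05.
- Test parent and adolescent separately, each at 0.05, only if the joint test is significant. For two reporters this is a closed procedure, so the family-wise rate stays at 5% when the joint test holds its level.
- Claim efficacy only if the effects favour the aids. The joint test has no direction and could reject when one reporter improves and the other worsens.
- Report all other decision process and quality measures and time points as secondary or exploratory differences with 95% confidence intervals and no efficacy claim.
- Disclose that the choice was made after recruitment.

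In 10.4, do not attach the existing figures to this contrast. They describe a single mean difference and do not reproduce at 15 per phase. Recompute them for the named test.

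Cost: wording and one new power calculation, with no new data or families. A significant result on another measure can no longer be a primary finding, and the joint test has somewhat less power than a single-reporter test if only one family member benefits.

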## 10. Number of Subjects

### 10.1. Total number of subjects to be enrolled locally:

**Aim 1:** We anticipate recruiting about 100 clinicians (inclusive of pediatricians and family medicine providers) and 200 parent-adolescent dyads.

**Aim 2:** We anticipate recruiting about 20 dyads (parent-adolescent) for semi-structured interviews and 20 dyads (parent-adolescent) or triads (parent-adolescent-clinician) for usability testing.

**Aim 3:** We anticipate recruiting about 20 clinicians (inclusive of pediatricians and family medicine providers).

**Aims 4a and 4b:** We anticipate recruiting about 40 dyads (parent-adolescent) (i.e. 20 per phase) and 20 healthcare providers (Aim 4b only).

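### Section 14.1 gives all three Time 3 secondary outcomes one logistic model; any outcome collected as a score or amount should be analysed on that scale

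*Combined protocol and SAP*

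**What the plan says.** Section 14.1 (Aim 4a and b) puts the secondary outcomes under one sentence. It opens "Secondary analyses related to health behaviors (contact sport participation and physical activity) and health status outcomes at Time 3 will be compared", and its closing part, which names the method, reads "health status outcomes at Time 3 will be compared between treatment and control conditions using logistic regression". The primary outcomes are treated differently: "Differences in primary decision process and quality outcomes will be compared between treatment and control conditions using Structural Equation Modeling".

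The documents name no instrument for physical activity or health status. They give no scale, category definition or cut-point, and do not say whether the logistic model is binary or ordinal or which covariates it carries. The survey forms are attachments held elsewhere. Time 3 appears to be the survey 3 months after the initial visit (sections 5.2 and 5.4).

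On size, section 10.4 plans 20 families per phase; "allowing for 15% attrition an estimated 17 per phase would complete the study". It then bases power for decisional regret on a lower figure: "Conservatively estimating 15 families per phase". No power figure is given for the secondary outcomes.

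The note on the first page says that, because fewer participants were recruited, the analysis was simplified to centre on comparing the conditions on the primary decision-related outcomes, with no subgroup comparisons. Section 14.1 still contains the secondary analyses.

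**The concern.** Contact-sport participation can be read as a yes/no outcome, and logistic regression is a natural model for it. Physical activity and health status are often recorded as amounts, scores or ordered ratings. If that is so here, binary logistic regression can be fitted only after each is split in two.

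Two things would then be at stake. A split discards the differences within each half, which a study of 15 to 20 families per phase can ill afford. And with no cut-point in the plan, the split could be chosen after the data are seen. A cut far from the centre can also leave a phase with everyone on one side, in which case ordinary logistic regression has no finite estimate.

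**Working it through.** **Inputs from the documents.** 20 families enrolled per phase, 15% attrition, 15 per phase as the conservative figure, alpha 0.05 (section 10.4). Completers: 20 × 0.85 = 17, as the plan states.

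**Inputs assumed.** A normal outcome with equal SD in both phases, a two-sided test, and a true difference of 1.06 SD. That value is chosen because a t-test has 80% power for it at 15 per phase; it is not a figure from the plan. The plan's only power statement concerns decisional regret: 7.1, 3.0 and 1.2 points for SD 12, 5 and 2, that is 0.59–0.60 SD. It does not reproduce at 15 per phase. The two-sided t-test values are 12.7, 5.3 and 2.1 points (1.06 SD each). That is a separate matter, and nothing below depends on it.

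**Power on the measured scale.** Noncentral t with noncentrality d√(n/2) and 2n − 2 degrees of freedom:
- n = 15: 1.06 × √7.5 = 2.903, critical t 2.048, power 0.800.
- n = 17: 1.06 × √8.5 = 3.090, critical t 2.037, power 0.850.
- n = 20: 1.06 × √10 = 3.352, critical t 2.024, power 0.904.

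**Power after a split, by formula.** A fixed cut midway between the two means lies 0.53 SD from each. The proportions above it are Φ(−0.53) = 0.298 and 0.702, a difference of 0.404. At n = 15, the standard error under no difference is √(0.25 × 2/15) = 0.1826, and under the alternative √(2 × 0.298 × 0.702/15) = 0.1670. Power = Φ[(0.404 − 1.96 × 0.1826)/0.1670] = Φ(0.277) = 0.61. Cuts at the 50th, 70th and 80th percentiles of the control phase give 55–61% by the same formula.

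**Power after a split, by simulation.** Likelihood-ratio test from a logistic model with phase as the only covariate, 40,000 trials per setting, difference 1.06 SD:

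| n per phase | t-test | Split at pooled sample median | Fixed midpoint cut |
|---|---|---|---|
| 15 | 80% | 53% | 60% |
| 17 | 85% | 64% | 70% |
| 20 | 90% (91% simulated) | 66% | 73% |

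The loss is 20–27 points at 15, 15–21 at 17 and 17–24 at 20. The two split columns differ partly because a sample-median split makes the test conservative: its actual type I error is 2.6%, 3.8% and 2.5% at 15, 17 and 20, against about 5% for the t-test. The fixed cut runs at about 4.3%, 5.7% and 4.1%.

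**Open cut-point.** With no true difference and 15 per phase, taking the best of cuts at the pooled 25th, 50th and 75th percentiles gives about 8% false positives, against 2.6% for the median split alone.

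**Empty cells at 15 per phase.** For a yes/no outcome with the same true rate p in both phases, the chance that at least one phase is all-no or all-yes is 1 − [1 − p¹⁵ − (1 − p)¹⁵]². This is 71% at p = 5%, 37% at 10% and 7% at 20%. The documents give no rates, so these show a range only. For a graded outcome with a 1.06 SD difference, cut at the control 30th percentile, the proportions above are 0.70 and 0.943; since 0.943¹⁵ ≈ 0.42, the chance is 42%.

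**The case against.** A reader might infer that the plan forces graded outcomes into two categories and discards information already collected. The documents do not support that. They never say physical activity or health status is graded or will be dichotomised, and they do not exclude an ordinal logistic model. If the items are yes/no, binary logistic regression is appropriate and the power argument falls away. This stands, and it makes the point conditional.

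A reader might also take 15 per phase as the analysed size and 53% as the loss. The first is the conservative figure for decisional regret; 17 completers are expected. The first page says the recruited sample was smaller but gives no number. The 53% belongs to one kind of split whose test runs below its nominal error rate. A prespecified or instrument-defined threshold near the midpoint gives about 60%. Hence the ranges above.

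Finally, the first-page note may mean these analyses are no longer planned. It does not say they were dropped, and 14.1 still lists them. They are secondary in any case, in what section 1.1 calls a pilot, so no primary conclusion rests on them.

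What remains is that 14.1 names one model for three outcomes without tying it to how each is measured.

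**Conclusion.** The point holds in conditional form. Section 14.1 names logistic regression as the only model for all three Time 3 secondary outcomes, with no scale, cut-point or model type. If physical activity or health status is a score or amount and binary logistic regression is used, power for a 1.06 SD difference falls from 80% to about 53–60% at 15 per phase, from 85% to about 64–70% at 17, and from about 90% to about 66–73% at 20. These figures assume a normal measure and depend on where the cut falls. The documents do not establish that any dichotomising will take place. Because the outcomes are secondary, this is a minor improvement.

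**What to change.** First reconcile section 14.1 with the first-page note: say whether the secondary Time 3 analyses are retained.

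If they are, replace the single method with a rule that each outcome is analysed on the scale collected:
- yes/no items: logistic regression, with Firth penalisation or an exact method if a cell is empty or sparse;
- ordered categories: proportional-odds regression;
- scores or amounts: linear regression.

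Name the instrument and scale for each outcome, and report each cohort difference with a 95% interval. If a threshold is wanted for interpretation, state it in advance.

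The cost is a few lines in 14.1. It needs no extra data or participants, and an item already collected as yes/no keeps its logistic model.
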